2.1.3 Primary Objective

To describe outcomes at 1, 2, 3, 6 and 12 months in infants and children with ChILD.

Outcomes measured will be

- death,
- survival on artificial ventilatory support (invasive or non-invasive),
- survival in supplemental oxygen,
- survival breathing room air,
- quality of life (QoL)

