2.1.4 Secondary Objectives

To describe variance in outcome at 1, 2, 3, 6 and 12 months in infants and children with ChILD according to

1. Diagnosis and Presentation
 - a. Diagnosis (Peer Review)
 - b. Diagnostic certainty (Peer Review)
 - c. Computed Tomography (CT) score – by component radiologist (Peer review)
 - d. Blood Oxygen Saturation (SpO₂) at rest in room air at presentation
 - e. SpO₂ asleep in room air at presentation (nadir)
 - f. Respiratory Rate (RR) (z score) at rest in air at presentation
 - g. Heart rate (HR) (z score) in air at presentation

- h. Blood pressure at rest for 5 minutes at presentation
 - i. Weight (z-score) at presentation
 - j. Leland Fan 5 point severity score (Nil, symptoms, SpO₂ <90% air asleep, SpO₂ at rest, Pulmonary Hypertension).
 2. Time to treatment and improvement
 - a. Time from onset of symptoms/signs of ChILD to first treatment
 - b. Time from onset of symptoms/signs of ChILD to diagnosis (local clinical)
 - c. Time from onset of symptoms/signs of ChILD to normoxia whilst awake (SpO₂ ≥94% breathing room air at rest)
 - d. Time from onset of symptoms/signs of ChILD to respiratory rate in normal range for age (Fleming, Thompson et al. 2011)
 - e. Time from onset of first treatment to reduction in RR by 10%
 - f. Time from onset of first treatment to reduction in HR by 20%
 - g. Time from onset of symptoms/signs of ChILD to normoxia whilst asleep (SpO₂ ≥94% breathing room air at rest)
 - h. Time from onset of symptoms/signs of ChILD to weight appropriate for age/height without use of calorie supplementation
 - i. Time from onset of treatment to improvement in weight by 10%
3. Treatments
 - a. Steroids
 - i. Use of steroids
 - ii. Dose, route and frequency of steroid use
 - iii. Time from first presentation to initiation of steroids
 - iv. Number of concomitant ChILD treatments at time of starting steroids
 - b. Hydroxychloroquine
 - i. Use of Hydroxychloroquine
 - ii. Dose and frequency of hydroxychloroquine
 - iii. Time from first presentation to initiation of hydroxychloroquine.
 - iv. Number of concomitant ChILD treatments at time of starting hydroxychloroquine
 - c. Azithromycin
 - i. Use of Azithromycin
 - ii. Dose and frequency of Azithromycin
 - iii. Time from first presentation to initiation of Azithromycin.
 - iv. Number of concomitant ChILD treatments at time of starting Azithromycin
4. Concomitant Medicines
5. Follow up Review
 - a. SpO₂ in room air measured 4 weeks after commencing initial treatment

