 - b. RR at rest measured 4 weeks after commencing initial treatment
 - c. Heart rate at rest measured 4 weeks after commencing initial treatment

6. Quality of Life score - PEDS QL Generic Core Scales
 - a. At 0 and 12 months.
7. Questionnaire for health care utilisation and costs
 - a. utilisation of inpatient and outpatient care to calculate direct costs gathered at 0, 3, 6 and 12 months
 - b. loss of productivity of parents and children to calculate indirect costs gathered at 0, 3, 6 and 12 months

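### The RR and HR improvement endpoints (Protocol 2.1.4, items 2d to 2f) set no condition on respiratory support, so a fall caused by starting oxygen or ventilation can count as improvement

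*Protocol*

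**What the plan says.** Section 2.1.4 of the Protocol groups nine items under a heading on time to treatment and improvement, and section 2.2.2 makes the contents of 2.1.4 the secondary endpoints. Three of the nine concern RR or heart rate (HR):

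- 2d: "Time from onset of symptoms/signs of ChILD to respiratory rate in normal range for age"
- 2e: "Time from onset of first treatment to reduction in RR by 10" per cent
- 2f: "Time from onset of first treatment to reduction in HR by 20" per cent

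None of the three mentions oxygen, ventilation or room air. Neighbouring items do. At presentation the Protocol asks for "Respiratory Rate (RR) (z score) at rest in air at presentation" (1f) and "Heart rate (HR) (z score) in air at presentation" (1g). The two saturation endpoints, 2c and 2g, apply to a child "breathing room air at rest", and the 4-week saturation in 5a is also in room air. The 4-week RR in 5b is "RR at rest measured 4 weeks after commencing initial treatment", with no mention of air, and the 4-week HR in 5c is worded in the same way.

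The primary objective (2.1.3) expects some children to be on support at follow-up. Its outcome states include "survival on artificial ventilatory support (invasive or non-invasive") and survival in supplemental oxygen. The schedule in section 3 records Outcome, HR, RR, SpO2 and Treatment together at weeks 4, 8, 12, 26 and 52.

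**The concern.** RR and HR are useful signs of improvement only if the child is producing them under comparable conditions. On controlled ventilation the respiratory rate is largely a machine setting. Oxygen or non-invasive support may also lower RR and HR without any change in the underlying disease. With no condition on support, 2d to 2f cannot separate a child who is getting better from one who got worse, was put on support and now has a lower rate.

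One event can therefore be scored in opposite directions at the same visit: as a poor state on the primary objective and as improvement on a secondary endpoint. Section 8.2 plans to describe changes over time by treatment and diagnosis, to model factors related to outcome, and possibly to compare response rates between two periods. Any difference in the use of support between groups or periods could enter those results as an apparent difference in improvement.

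**Working it through.** The Protocol gives no figure to reproduce: section 8.1 states that no sample size calculation is possible, and there is no alpha, power or effect size. The check compares conditions item by item and then works through one case.

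**Step 1. Conditions side by side (Protocol 2.1.4).**

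| Item | Measure | Condition stated |
|---|---|---|
| 1f | RR at presentation | rest, air |
| 1g | HR at presentation | air |
| 2c, 2g | normal saturation, awake and asleep | rest, room air |
| 2h | weight appropriate for age/height | no calorie supplements |
| 5a | saturation at 4 weeks | room air |
| **2d** | RR in normal range | **none** |
| **2e** | RR down 10% | **none** |
| **2f** | HR down 20% | **none** |
| 5b, 5c | RR and HR at 4 weeks | rest only |

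The list controls for support where saturation is concerned, and for nutritional support in 2h, but not for RR or HR after presentation. No other section supplies the missing condition.

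**Step 2. When the criteria are met.** Threshold = starting value × (1 − required fall).

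- The Protocol's background (1.1) mentions rates as high as 80/min. For 2e, 80 × 0.90 = 72/min.
- With an assumed start of 60/min, 60 × 0.90 = 54/min.
- For 2f, with an assumed start of 150/min, 150 × 0.80 = 120/min.

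**Step 3. A child moved onto support.** Fall = (start − new) / start. The new values are assumptions, since the Protocol gives none.

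- Ventilated at a set rate of 30/min, start 80/min: (80 − 30) / 80 = 62.5%.
- Same set rate, start 60/min: (60 − 30) / 60 = 50%.
- RR of 70/min after oxygen is started, start 80/min: (80 − 70) / 80 = 12.5%.

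All three exceed 10%, so 2e is met. The result is not sensitive to the assumed ventilator rate: any rate up to 72/min (start 80) or 54/min (start 60) meets 2e. Whether 2d is also met depends on the child's age and the rate. Whether 2f is met depends on whether HR falls by a fifth.

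**Step 4. The rest of the same visit.** The Outcome entry reads alive on ventilation or alive in oxygen. Items 2c and 2g cannot be met, because they require room air. The Protocol's own improvement endpoints therefore disagree about this child, and the missing condition is the reason.

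**Step 5. Does the reading of 2.1.4 matter?** Section 2.2.2 treats the items as endpoints, while the opening line of 2.1.4 treats them as factors by which variation in outcome is described. As endpoints, deterioration can be scored as improvement. As factors, the factor is partly produced by the outcome it should explain, because going onto ventilation changes RR. The gap matters either way.

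**The case against.** The strongest reply is that this belongs in the statistical analysis plan. Section 8.2 promises one with full statistical detail, written before the data are seen, and support status is recorded at the same visits as RR and HR, so nothing prevents a derivation rule there. It is true that such a plan could repair the problem. But the Protocol does not leave the measurement condition open: it fixes it for some items in the list and omits it for others, and the criterion as written gives the wrong classification.

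A second reply is that these are mainly descriptive items and that a ventilated child remains visible as ventilated in the Outcome data. This limits the harm but does not correct the improvement endpoint.

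Three further objections limit the point and stand:

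- The Protocol never labels such a child a treatment responder. It speaks of improvement, and of response rates that it does not define and would only possibly compare, between periods.
- Item 2d runs from symptom onset; of the three, only 2e and 2f are timed from treatment.
- Items 5b and 5c are single measurements with no improvement threshold, so nobody is misclassified on them. They share the missing condition and no more.

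A reader might also infer that the error favours the most heavily treated children, on the ground that the sickest receive both the most drugs and the most support. The Protocol says nothing on either link. Nor does it show that oxygen reliably lowers RR or HR; a deteriorating child newly on oxygen may have an unchanged or higher rate.

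**Conclusion.** The point holds as a defect of definition in 2d, 2e and 2f. As written, a child whose RR or HR falls because support was started can be counted as improved at the visit that records survival on that support. This rests on the text and on one general premise, that controlled ventilation largely sets the respiratory rate. The example rates only illustrate it.

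The size of the effect is unknown. A reader might want a count: 130 children per year over 30 months is 130 × 2.5 = 325, and if 10% to 20% stepped up support by week 4, that would be about 33 to 65 children. The Protocol does not support using this as an error count. The step-up rate is assumed, 325 supposes that every possibly eligible child is recruited throughout a hoped-for period, and not every child who steps up would cross a threshold. The direction of any bias between treatments is equally undetermined.

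The matter concerns secondary endpoints of a descriptive study. It should be corrected, but it does not undermine the primary objective.

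**What to change.** State the measurement condition in section 2.1.4:

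- **2e and 2f:** count a value as improvement only if it is taken at rest, with the child breathing spontaneously, on no more respiratory support than at the start of first treatment.
- **2d:** count a value only if the child is breathing spontaneously at rest in room air, which matches 2c.
- **Values on greater support:** these do not count at that visit, but the child stays at risk and can meet the criterion later. Only death is a competing event. Making a step-up in support a competing event would discard a child who was ventilated early and later recovered within the 12 months.
- **5b and 5c:** report RR and HR together with the support in use at the measurement.

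These rules decide which recorded values count. They do not ask for any child's support to be changed for a measurement.

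There are two costs. Observed improvement rates will fall somewhat. One item must also be recorded: the support in use at the start of first treatment and at each RR and HR measurement. The Outcome row helps from week 4 onwards, but the schedule shows no Outcome entry before then, so support at the reference point is not shown as collected. A visit-level outcome state also need not be the support in use when the rate was counted, for example in a child ventilated only at night.

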6 STUDY ASSESSMENTS

The study assessments are detailed in the study design, section 3

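### Items 2e, 2f and 2i time a percentage change in RR, HR and weight from the start of treatment, but the protocol requires no reading of any of the three at that point

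*Protocol*

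**What the plan says.** Protocol section 2.1.4 (Part B secondary objectives) contains three items that run from treatment start to a percentage change:

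- 2e: "Time from onset of first treatment to reduction in RR by 10" per cent
- 2f: "Time from onset of first treatment to reduction in HR by 20" per cent
- 2i: "Time from onset of treatment to improvement in weight by 10" per cent

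None states the value against which the percentage is judged. The early values that the same section names all belong to presentation: "Respiratory Rate (RR) (z score) at rest in air at presentation" (1f), "Heart rate (HR) (z score) in air at presentation" (1g) and "Weight (z-score) at presentation" (1i).

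On what is collected and when, section 6 says only: "The study assessments are detailed in the study design, section 3". The section 3 table has seven time points: study entry, peer review, and weeks 4, 8, 12, 26 and 52. HR and RR are marked at the five follow-up visits only. No column is tied to the start of treatment, and weight has no row. A participant's time in the study begins at signed consent.

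The interval between presentation and treatment is itself a variable to be described, for example "Time from first presentation to initiation of steroids" (3a iii), with parallel items for hydroxychloroquine and azithromycin.

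**The concern.** A percentage change timed from an event needs a value at, or shortly before, that event. Here the clock starts at treatment, while the only early value the protocol names comes from presentation. If the child's condition moves between the two, a change measured from presentation combines what happened before treatment with what happened after it. A child who settled before the first treatment would need less further improvement to qualify. A child who worsened and was then treated would need more.

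Section 1.2 says that Part B is meant to inform on responses to treatment in the first year, and these three items are its percentage-change measures timed from treatment. The gap lies in data collection, so it belongs in the protocol. An SAP can name a baseline, but it cannot supply a reading that nobody was asked to record.

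**Working it through.** The protocol gives no numerical target, variance or sample size for these items (section 8.1 says that no sample size calculation is possible), so there is no stated figure to reproduce. The check has two parts.

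**1. Is a treatment-start reading required anywhere?**

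- Section 3 table: HR and RR at weeks 4, 8, 12, 26 and 52; no treatment-start column; no weight row.
- Registration dataset (notes to the table): symptoms, signs, hypoxaemia, radiology and duration; no numeric RR, HR or weight is named.
- Peer Review dataset: described as complete, but not itemised for RR, HR or weight. Section 7 says that the initial referral data form the referral for peer review, so this dataset is not tied to treatment start.
- Items 5a to 5c: SpO2, RR and HR four weeks after initial treatment begins; no matching value at its start.
- Section 7(a): hospital records are a data source, but no value at treatment start has to be extracted from them.

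No reading at treatment start is required. For 2i, no follow-up weight is scheduled either.

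**2. What happens if the presentation value is the reference?**

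Let P be the value at presentation and d the proportional drift before treatment, so that the value at treatment start is P(1 + d). Let T be the target ratio: 0.90 for RR, 0.80 for HR, 1.10 for weight. The target against presentation is T × P, so the change needed from the treatment-start value is

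T × P / [P(1 + d)] − 1 = T/(1 + d) − 1.

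The values of d are assumptions; the documents give none.

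| Assumed drift d | RR (T = 0.90) | HR (T = 0.80) | Weight (T = 1.10) |
|---|---|---|---|
| −10% | 0.0% | −11.1% | +22.2% |
| −5% | −5.3% | −15.8% | +15.8% |
| 0% | −10.0% | −20.0% | +10.0% |
| +5% | −14.3% | −23.8% | +4.8% |
| +10% | −18.2% | −27.3% | 0.0% |

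For example, 0.90/1.10 − 1 = −18.2% and 0.90/0.90 − 1 = 0.

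In breaths per minute, take an illustrative RR of 60 at presentation, so the target against presentation is 0.90 × 60 = 54.

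- RR is 54 when treatment starts: the presentation target is met with no further change. The target from treatment start would be 0.90 × 54 = 48.6.
- RR is 66 when treatment starts: a fall to 0.90 × 66 = 59.4 is a 10% response to treatment, but it does not reach 54.

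With the reference taken at treatment start, the required changes are the nominal −10%, −20% and +10% whatever the drift.

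**The case against.** The strongest reply is that choosing a baseline is ordinary SAP content, that section 8.2 promises an SAP, and that a suitable value may well exist. Hospital records are a named source, and section 5.2 expects most children to be in-patients. The content of the Peer Review dataset is not itemised. A child first treated after week 4 would already have scheduled RR and HR readings. This stands as far as it goes: the absence of a named reference would not, alone, be a finding. It does not answer the point that no reading near treatment start is required, so its availability is left to each site and each chart.

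Three stronger readings are tempting, and the documents do not support them.

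- A reader might infer that presentation is the only possible reference. The protocol never assigns it that role. It is only the one early value named.
- A reader might infer that a child who settled before treatment would be counted as a responder on day 0. Without a reading that day, no event can be dated to it; on the schedule it would first be seen at a follow-up visit.
- A reader might want to state the share of children misclassified. The documents give neither within-child variability nor drift. Any share that arises with zero drift is reading-to-reading noise, which a single pre-treatment reference would carry as well.

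Nor does section 8.2 plan a comparison between sites, so harm to such a comparison should not be claimed.

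**Conclusion.** The point holds in a conditional form. The protocol requires no RR, HR or weight at treatment start, although 2e, 2f and 2i are timed from there, and for 2i it schedules no weight at follow-up. If the presentation value is used as the reference, the effective threshold depends on what happened before treatment. A prior drift of 10% in either direction moves the required RR change from −10% to 0% or −18.2%, and the required HR change from −20% to −11.1% or −27.3%.

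The size rests entirely on the assumed drift and on the use of presentation values. At zero drift the two references agree, and if treatment follows presentation promptly the effect is likely to be small. The protocol gives no length for the interval, but by listing it as a variable it does not treat it as fixed.

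These are secondary descriptive items. The primary outcomes (death, ventilatory support, oxygen, room air, quality of life) are unaffected. The change should be made, but the study does not stand or fall on it.

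**What to change.** - Add a CRF entry, filled from the hospital chart, for the last RR, HR and weight before the first treatment, with the date of each reading and the respiratory support at the time.
- State in 2e, 2f and 2i that the percentage change is taken from these values. Report 5b and 5c as change from them as well, and 5a too if SpO2 is recorded in the same entry.
- Where only a presentation value exists, flag the case and do not pool it silently with the others.
- Add a weight row to the follow-up visits in the section 3 table, so that 2i can be measured.

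The cost is one CRF block, one schedule row and a wording change in section 2.1.4, with some missing values where charts hold no reading before treatment. The pre-treatment values need no extra visit, and nothing here changes care.

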2.2.1 Primary Endpoint

12-month review or time to death.

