3 STUDY DESIGN

Part A: ChILD-EU Database and Biobank

A web-based data capture system and a Biobank of cases of ChILD, based on SecuTrial®, has been built as an extension of an existing database located in Munich. Appendix 1 has a more detailed description of the database.

Biomaterials will be located in Munich and will at least include, where possible, as a minimum blood (plasma, serum, or EDTA), CT chest images and tissue biopsy samples from patients with proven ChILD. All biomaterials will be obtained during diagnostic or therapeutic procedures and only otherwise dispensable material will be collected.

All cases will undergo International Peer Review to confirm or suggest alternative expert opinion diagnosis. Cases where an alternative diagnosis is considered most likely by the International Peer Review team will not enter the Observational Trial, but data collected up to that point will be retained for future case review and standardisation.

Part B: ChILD-EU Observational Study

12-month multi-centre observational study.

Consent will be sought to begin observations from time of presentation at hospital during which the diagnosis is made. Participants will commence in the study from the point of signed informed consent and will continue in the trial for 12 months.

It is anticipated that data will be collected at seven time points, summarised in the following table.

Every effort should be made to see a participant as close as possible to the scheduled time point. If the visit occurs outside of the recommended visit window then a justification may be sought.

At 12 months, the observational study will be completed but clinicians and parents will be invited to continue providing minimal dataset information on an annual basis.

	Study entry ^(A)	Peer review ^(A)	4 (+/- 1) week	8 (+/- 1) week	12 (+/- 2) week	26 (+/- 4) week	52 (+/- 4) week ^(A)
Registration dataset	X						
Peer Review dataset		X					
Outcome			X	X	X	X	X
HR			X	X	X	X	X
RR			X	X	X	X	X
SpO2			X	X	X	X	X
Treatment			X	X	X	X	X
Spirometry ^(B)			X	X	X	X	X
QoL		X					X
Utilisation of health care		X			X	X ^(A)	X
CXR ^(C)						X	X
Review of case and diagnosis		X					X

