8.2 PROPOSED ANALYSES

Part A: ChILD-EU Database and Biobank

There will be descriptive statistics of cases and outcomes only.

Part B: ChILD-EU Observational Study

Analysis [1st 12 months]

Initial analysis will be descriptive presenting changes over time in characteristics measured broken down by key variables of interest such as type of treatment, diagnosis etc. To determine what factors are related to outcome we will model outcome with collected data taking into account likely covariates. If appropriate we will consider missing data using the guidelines from www.missingdata.org.uk.

Analysis [2nd 12 months]

Repeat of the same type of analysis as for 1st period. Possibly with addition of comparisons of response rates between two periods

The study will have a statistical analysis plan containing full details of the statistical aspects of this study produced by the trial statistician prior to seeing the data.

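### Outcome, including death, is described by drug use and by time to starting the drug, yet exposure is not required to precede the outcome period, so surviving to the start is built into both factors

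*Protocol*

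**What the plan says.** Section 2.1.4 of the protocol opens its list of factors with "To describe variance in outcome at 1, 2, 3, 6 and 12 months in infants and children with ChILD according to". Item 3 of that list names, for steroids, "Use of steroids" and "Time from first presentation to initiation of steroids". The same pair is repeated for the other two drugs, for example "Use of Hydroxychloroquine". No time point is attached to use.

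Death is among the outcomes in section 2.1.3, and the primary endpoint in section 2.2.1 is "12-month review or time to death". On follow-up, section 3 says: "Participants will commence in the study from the point of signed informed consent and will continue in the trial for 12 months". Its visit table records treatment at weeks 4, 8, 12, 26 and 52, so starts during follow-up are expected.

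Section 8.2 plans for Part B a description of change over time "broken down by key variables of interest such as type of treatment, diagnosis etc". It then plans a model of outcome on the collected data, with likely covariates, to find the factors related to outcome. Full statistical detail is left to an analysis plan that is not shown.

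**The concern.** A child who dies before a drug is started can only be counted as a non-user and has no time to initiation. A child who starts at month 6 has, by definition, lived six months. So for any drug started after entry, the grouping is partly decided by the outcome. A start after month 1 also cannot bear on the month-1 outcome that the same objective lists.

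This immortal-time bias is separate from confounding by severity. Adjusting for baseline covariates, as section 8.2 foresees, does not remove it, because the fault lies in when exposure is defined and not in who is exposed. By itself it makes use look better than no use and late starting look better than early starting. Section 1.2 says that Part B is to give data on outcome in relation to standard interventions and to guide further research. A table of deaths by drug use, or by delay to starting, would be read in that light.

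**Working it through.** **What the documents give.** There is no sample size, power, mortality or start-time figure, so there is no plan figure to reproduce. Section 1.1 says only that some presentations lead to early death. Everything below rests on stated assumptions, with no drug effect, so the true risk ratio is 1 throughout.

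**A case that can be checked by hand.** Assume 12-month mortality m = 20% with constant hazard, a share s = 70% of children destined for the drug, and an exponential start time with median 1 month, independent of risk.

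- Death hazard h = -ln(0.80)/12 = 0.0186 per month. Start hazard g = ln(2)/1 = 0.693 per month.
- Users (start before death and before month 12): s × g/(g+h) × [1 - exp(-12(g+h))] = 0.7 × 0.9739 × 0.9998 = 0.6816 of the cohort.
- Users alive at 12 months: s × [1 - exp(-12g)] × (1-m) = 0.7 × 0.9998 × 0.80 = 0.5599.
- Death risk in users: 1 - 0.5599/0.6816 = 17.9%.
- Non-users: 1 - 0.6816 = 0.3184, of whom 0.80 - 0.5599 = 0.2401 are alive. Death risk: 1 - 0.2401/0.3184 = 24.6%.
- False risk ratio: 17.9/24.6 = 0.73. Simulation gives 17.9% against 24.5%, also 0.73.

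**Range by simulation.** Up to 2,000,000 children per scenario, 70% destined for the drug. Late means started after month 3, early means within month 1. Front-loaded deaths follow a Weibull distribution with shape 0.5.

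| Median start | Use vs no use, constant hazard, mortality 5-30% | Use vs no use, front-loaded, mortality 15% | Late vs early, constant hazard | Late vs early, front-loaded |
|---|---|---|---|---|
| 0.25 months | 0.90-0.92 | 0.66 | too few late starters | too few late starters |
| 1 month | 0.70-0.75 | 0.45 | 0.67-0.70 | 0.50 |
| 3 months | 0.46-0.55 | 0.31 | 0.52-0.57 | 0.39 |

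A wider grid used mortality 10%, 15% or 25%, Weibull shape 0.5 to 1, and 50% or 70% destined. For median starts of 1-3 months, the risk ratio for use is about 0.29-0.82 (0.31-0.80 at 15% mortality). For a median start of about one week it is about 0.64-0.95.

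**Do the remedies work?** Grouping children alive at month 1 by drugs started by then returns 0.98-1.02. A time-dependent exposure analysed as crude person-time rates returns 0.98-1.01 under constant hazard. With front-loaded deaths it still gives 0.57-0.67. Exposed and unexposed children must therefore be compared at the same time since entry.

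**Adding confounding by indication.** Assume that 30% of children are sicker (12-month mortality 40% against 5%).

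- Sicker children treated more often (90% against 60%) and sooner (median 0.5 against 2 months): use vs no use 1.45, late vs early 0.13.
- More extreme (95% against 40%; median 0.25 against 3 months): use vs no use 2.82, late vs early 0.08.

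The use contrast can reverse, while the late-starting contrast becomes more misleading.

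**The case against.** The strongest reply is that section 2.1.4 lists topics and not a model. It does not define use as ever-use and does not bar updating exposure over time. Landmarks and time-dependent covariates are ordinary content for an analysis plan. Section 2.2.2 treats the 2.1.4 items as secondary endpoints, and the list contains plain results such as time to normoxia, quality of life and costs. On that reading, time to initiation simply describes practice. This stands in part. It is a reason for a lower severity, and no one can infer that the analysis plan lacks a suitable method. But the objective as worded sets outcome against use and against delay, and an analysis plan that follows it literally inherits the fault.

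A reader might infer that an inert drug would appear to lower mortality in this study. The documents do not support that. It is the direction of this bias alone, and treating sicker children more often could make use look harmful.

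The size is also open. Consent is sought at the hospital presentation where the diagnosis is made, and section 5.2 expects most children to be in-patients, so many starts may fall close to entry and the bias would then be smaller. Starts before consent create no immortal time within follow-up. They raise delayed entry instead. That is also the main issue with the related item 2a, "Time from onset of symptoms/signs of ChILD to first treatment", which a reader might otherwise count as a further instance of the same bias.

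Finally, only death was simulated. The effect on support state and quality of life was not quantified.

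**Conclusion.** The point holds for drugs started after study entry. As worded, item 3 and section 8.2 relate outcome to factors that depend on surviving to the start, and covariate adjustment does not correct this. With no drug effect and starting unrelated to risk, the false death risk ratio for use is about 0.29-0.82 for median starts of 1-3 months and 10-25% mortality. It is about 0.64-0.95 for a median start of about a week. These ranges rest wholly on assumed mortality, hazard shape and start times. The net direction for use against no use cannot be stated, because confounding by indication may oppose it. The bias towards late starting remained in each confounding scenario examined. Because the objective is secondary and descriptive and the analysis plan is not shown, this should be fixed but does not undermine the study.

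**What to change.** In section 2.1.4 item 3 and section 8.2, state that outcome will be related to treatment in one of two ways.

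- **Time-dependent exposure**, compared at equal time since entry. An example is a Cox model with each drug as a time-dependent covariate, with allowance for drugs started before consent. Crude person-time rates are not enough.
- **Landmarks**: group children alive at a visit by the drugs started by then, describe only later outcomes, and report earlier deaths separately. Use more than one landmark, for example weeks 4 and 12, so that later starters are not all counted as unexposed.

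Report time to initiation as a description of practice, by the cumulative incidence of starting with death as a competing event, and not as a predictor of outcome.

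The cost is wording in the protocol and the analysis plan. The start dates are already needed for item 3. The drawback of a landmark is that deaths before it, and the outcome at the landmark visit itself, drop out of the treatment comparison. With a first landmark at week 4, the 1-month outcome would be described without a breakdown by treatment, and the text should say so.
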